2.3.4 Other Endpoints

2.3.4.1 PK Endpoints

- PK parameters of P1101 in plasma samples, including (but not limited to) time to maximum plasma concentration (Tmax), maximum plasma concentration (Cmax), and area under the time-concentration curve (AUC0-t).

PPK analysis will be conducted based on a separate SAP for the PK data of this study.

2.3.4.2 Immunogenicity Endpoints

- Proportion of subjects who are ADA positive and negative will be determined

2.3.4.3 Exploratory Endpoint

- Changes from baseline in the bone marrow, based on analysis of megakaryopoiesis (normal or increased; patterns of distribution, cellular shape, nuclear shape), age-related cellularity, granulopoiesis and erythropoiesis (decreased/normal/increased, presence of maturation defects), G/E ratio, fibers; % of CD34+ cells; other bone marrow abnormalities.

*Bone marrow histological remission defined as the disappearance of hypercellularity, trilineage growth (panmyelosis) and absence of >grade 1 reticulin fibrosis (optional)

- Molecular response

2.3.5 Multiplicity Adjustment

No multiplicity adjustment will be considered for this single arm study.

2.4 Determination of Sample Size

Sample size is calculated, based on the following assumptions;

- The target population of the Japanese local study: Japanese PV patients for whom the current standard of treatment is difficult to apply.
- Study design: P1101 single arm no controlled study.
- Primary study objective: To evaluate the safety and efficacy of P1101 for Japanese PV patients for whom the current standard of treatment is difficult to apply.
- Primary efficacy variable: Complete Hematological Response (CHR)
- Study period and evaluation visits: 3 months, 6 months, 9 months and 12 months. The safety follow-up will be continued to 12 months and the major efficacy data will be obtained at 12 months.
- The primary analysis of the primary endpoint: The lower limit of the 95% confidence interval of CHR rate is greater than 11%, and also the slope of the linear regression model of the CHR rate time over the course of the study is greater than 0 (positive trend):
- The rationale: the natural healing rate (placebo response) of CHR rate of PV patients is 0%, thus if the lower limit of 95% confidence interval of the CHR rate exceed 11%, the efficacy of P1101 can be confirmed. The rationale to set the CHR rate limit as 11% is, (1) 11% is the minimum CHR rate value of P1101 obtained in the PROUD-PV study, (2) and the trend of the CHR rate is positive, thus 11% can be considered as a limit of the acceptable clinical risks.
- Assuming the above conditions, the power of the study at 9 months will be about 85% with 25 cases (CHR rate of the PROUD-PV study at 3, 6, 9, and 12 months are 11%, 27%, 36% and 43%, respectively). Considering the uncertainty of maximum 5 patients who are different background from PROUD-PV, a total of 30 cases will be reasonable to evaluate both efficacy and safety.

3 General data handling and definitions

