## 9.1 Inclusion Criteria

1. Male or female patients  $\geq 20$  years old at the time of informed consent
2. Patients diagnosed with PV according to the WHO 2008 or WHO 2016 criteria
3. PV patients for whom the current standard of treatment is difficult to apply. Patients with a documented history of refractory to HU are excluded (see Appendix 6; modified ELN criteria based on "Barosi et al, 2010 ELN criteria", (Barosi et al. 2010)).
  - Younger patients (long-term treatment is anticipated)
  - Patients who are categorized as low risk, but cytoreduction is recommended due to disease-related signs and symptoms (headache, dizziness, pruritus, night sweats, fatigue, erythromelalgia, vision disorders, scintillating scotoma, early satiety, abdominal distension).
  - Patients with HU intolerance (see Appendix 6; modified ELN criteria based on "Barosi et al, 2010 ELN criteria", (Barosi et al. 2010))
4. Total HU treatment duration shorter than 3 years (cumulatively) at screening
5. For cytoreduction naïve patients only: PV in need of cytoreductive treatment, defined by fulfilling as one or more of the following criteria at baseline:
  - at least one previous well documented major cardiovascular PV-related event in the medical history
  - poor tolerance of phlebotomy (defined as a phlebotomy/ procedure-related adverse event causing significant adverse impact on the patient and limiting ability to apply phlebotomy with the intention to keep Hct  $<45\%$ )
  - frequent need of phlebotomy (more than one phlebotomy within last month prior entering the study)
  - platelet counts greater than  $1000 \times 10^9/L$  (for two measurements within the month prior treatment start)
  - leukocytosis (WBC  $>10 \times 10^9/L$  for two measurements within the month prior treatment start)
  - manifestation of disease-related signs and symptoms (headache, dizziness, pruritus, night sweats, fatigue, erythromelalgia, vision disorders, scintillating scotoma, early satiety, abdominal distension)
6. Adequate hepatic function defined as total bilirubin  $\leq 1.5 \times$  upper limit normal (ULN), international normalized ratio (INR)  $\leq 1.5 \times$  ULN, albumin  $>3.5 \text{ g/dL}$ , alanine aminotransferase (ALT)  $\leq 2.0 \times$  ULN, aspartate aminotransferase (AST)  $\leq 2.0 \times$  ULN at screening
7. Hemoglobin (HGB)  $\geq 10 \text{ g/dL}$  at screening
8. Neutrophil count  $\geq 1.5 \times 10^9/L$  at screening
9. Serum creatinine  $\leq 1.5 \times$  ULN at screening

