## 15.3 Assessment of Efficacy

### 15.3.1 Efficacy Measurements and Time Points

#### 15.3.1.1 Primary Efficacy Measurements – Peripheral Blood Count Remission

The primary efficacy endpoint is the phlebotomy-free complete hematologic responder rate (CHR) at month 9 and month 12.

The phlebotomy-free responder rate is defined as the proportion of patients with complete hematologic response (CHR) and with no phlebotomies during the previous 3 months.

A responder in sense of a primary endpoint is a patient who has met all of the following criteria at month 9 and month 12:

- • Hematocrit <45% phlebotomy-free (absence of phlebotomy during the previous 3 months)

- • Platelet count  $\leq 400 \times 10^9/L$ ,
- • WBC count  $\leq 10 \times 10^9/L$

Scheduled hematological assessments will occur as indicated in Appendix 1. Samples for hematology assessments will be prepared using standard procedures. For the hematologic parameters of Hct, platelets and WBCs, central laboratory assessments at Weeks 0, 12, 24, 36, and 52 will be used for determination of responder. Detailed specifications for hematology sample handling, shipping, and processing will be provided in a laboratory manual.

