4.3.4 Efficacy Variables and Analysis

4.3.4.1 Efficacy Variable

The primary efficacy endpoint is the proportion (CHR) of subjects who achieved the phlebotomy-free complete hematologic response at both month 9 and month 12 without phlebotomies during the previous 3 months. Specifically, subjects who meet all the following criteria at months 9 and 12 will be classified as responder:

- Hematocrit $<45\%$ phlebotomy-free (absence of phlebotomy during the previous 3 months)
- Platelet count $\leq 400 \times 10^9/L$,
- WBC count $\leq 10 \times 10^9/L$.

Subjects, who fails to meet all the criteria or withdraw early for any reason, will be classified as non-responder.

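### Entry criteria allow patients already in CHR before the first dose, and the SAP neither identifies them nor reports CHR without them

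*SAP*

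**What the plan says.** **Success rule.** SAP 2.4 has two conditions. The first is "The lower limit of the 95% confidence interval of CHR rate is greater than 11" per cent; the second is that "the slope of the linear regression model of the CHR rate time over the course of the study is greater than 0". The value 11% is used because "11% is the minimum CHR rate value of P1101 obtained in the PROUD-PV study". The statement that "the natural healing rate (placebo response) of CHR rate of PV patients is 0" per cent is offered as the reason why exceeding 11% confirms efficacy.

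**Entry.** Inclusion criterion 5 (Protocol 9.1) lists reasons for needing treatment but opens "For cytoreduction naïve patients only: PV in need of cytoreductive treatment". One item is enough, and two items (a past cardiovascular event, disease symptoms) involve no blood count or phlebotomy. Patients with under 3 years of cumulative HU may enter. Criterion 3 adds "Patients with a documented history of refractory to HU are excluded". No inclusion or exclusion criterion requires every patient to have a hematocrit, platelet or white-cell value outside the CHR limits, or a recent phlebotomy.

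**Response.** SAP 4.3.4.1 states that "subjects who meet all the following criteria at months 9 and 12 will be classified as responder", with no condition on status before treatment. Time to first response (SAP 4.3.4.2) runs from first dosing to the first visit at which the criteria are met, for all patients. The only planned split of response is by prior HU (SAP 4.3.4.2 and 4.3.5.2).

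**The concern.** In a single-arm trial the patient's state before treatment stands in for the control. If some patients start in CHR, the rate at Months 9 and 12 mixes patients who reached the state on P1101 with patients who kept it, and the 0% argument does not apply directly to the second group.

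Two routes lead into that group:

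- **HU-treated patients with controlled counts.** Appendix 6, item 4 describes intolerance as cytopenia at the HU dose that produces a complete or partial response, so the protocol itself recognises patients who are intolerant and responding. Appendix 7 keeps HU at its full baseline dose for the first two weeks of P1101, so such a patient can be in CHR at Week 0.
- **Naive patients who qualify on symptoms or a past cardiovascular event.** All three counts would have to be within limits with no phlebotomy for three months. This is possible but less plausible.

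At stake are how the headline rate is read against 11%, and the meaning of time to first response: a patient already in CHR can be given a first response at Week 12. The prior-HU split does not isolate the group. It pools controlled and uncontrolled HU patients and misses naive patients in CHR.

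**Working it through.** **Inputs.** Bar 11%, design rate 36% at Month 9, 25 cases for power and 30 planned (SAP 2.4); exact Clopper–Pearson 95% interval (SAP 4.3.5.1). The number of patients in CHR at baseline, k, and the share who keep it are not in the documents. I assume k = 1 to 3 with full retention in the table, then widen both.

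**Formula.** For x responders of n, the lower limit L(x, n) is the 2.5th percentile of Beta(x, n − x + 1). The interval condition is L > 11%.

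**The plan's own figure.** L(6, 25) = 9.4% and L(7, 25) = 12.1%, so 7 of 25 are needed. P(X ≥ 7 | n = 25, p = 0.36) = 85.2%, which matches the stated power of about 85%. That arithmetic is sound.

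**At 30 patients.** L(7, 30) = 9.9% and L(8, 30) = 12.3%, so 8 are needed. The chance of passing is 89.8% at a true 36% and 1.35% at a true 11%.

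**Removing baseline responders.** If the total is T and k baseline responders all remain in CHR, the other patients show (T − k)/(30 − k). Lower limits:

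| k | T = 8 | T = 9 | T = 10 | T = 11 |
|---|---|---|---|---|
| 1 | 7/29: 10.3% | 8/29: 12.7% | 9/29: 15.3% | 10/29: 17.9% |
| 2 | 6/28: 8.3% | 7/28: 10.7% | 8/28: 13.2% | 9/28: 15.9% |
| 3 | 5/27: 6.3% | 6/27: 8.6% | 7/27: 11.1% | 8/27: 13.8% |

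The trial passes while the remaining patients fall short at T = 8, and at T = 9 if k is 2 or 3. From T = 10 the remaining patients clear the bar too. The design rate implies 0.36 × 30 = 10.8, or about 11 responders.

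**Chance of meeting the interval condition.** Let the number retained follow Binomial(k, r) and responders among the others follow Binomial(30 − k, 0.11). The probability that the sum is at least 8, for r from 50% to 100%, is:

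- k = 0: 1.35%
- k = 1: 2.3% to 3.4%
- k = 3: 5.7% to 16.9%
- k = 5: 12.2% to 52.9%

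**Slope condition.** Patients in CHR at all four visits contribute nothing to the slope, so baseline responders alone give slope 0 and fail. With 3 constant responders and one more from Month 9, the visit rates are 3, 3, 4 and 4 of 30. The deviations of Months 3, 6, 9 and 12 from their mean are −4.5, −1.5, 1.5 and 4.5, so the slope is [(1.5 + 4.5)/30]/45 = 0.0044 per month, which is positive. SAP 2.4 asks only for a slope above 0, and SAP 4.3.5.2 says the slope is presented, with no test or interval.

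**Power of the supportive analysis at a true 36%.** It is 90.4% with 27 patients (7 needed) and 85.2% with 25 (7 needed).

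**The case against.** The other side has four substantial points.

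1. **Origin of the bar.** A reader might infer that the 11% value rests on the 0% rate and falls with it. It does not: 11% is the lowest P1101 rate in PROUD-PV, which Protocol 5.3 describes as covering HU-naive and currently treated patients. That benchmark may already contain baseline responders. This stands. The 0% statement supports only the inference from passing the bar to efficacy.
2. **HU withdrawal.** Appendix 7 has HU discontinued from Week 13, and Protocol 14.2 bars other cytoreductive therapy. A switched patient is about 36 − 13 = 23 weeks off HU at Month 9 and 52 − 13 = 39 weeks at Month 12. CHR then may be partly a real P1101 effect, and the objective never claims induction from a non-CHR state. This also stands. It is a reason to describe these patients separately, not to discount them; a single arm cannot divide the effect.
3. **Frequency.** A reader might infer that excluding HU-refractory patients leaves an HU group mostly in CHR. The documents do not show that. Appendix 6, items 1 to 3 define refractoriness only after 3 months at 2 g/day or more, so patients uncontrolled on less may enter, as may intolerant patients who have stopped HU.
4. **Existing outputs.** The prior-HU split, the target-value flags and the changes from baseline give some information, but none combines the three counts and phlebotomy history into a baseline CHR status.

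The slope condition is a further safeguard, though a weak one.

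**Conclusion.** The point holds as a gap in eligibility and reporting. Patients already in CHR can enrol, nothing in the SAP identifies them, and for them the 0% argument does not apply directly. Time to first response has the clearest defect, since a first response can be credited to a patient who already had one.

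The size cannot be computed from the documents. With 1 to 3 retained baseline responders, the overall result and the result in the other patients diverge only at a total of 8, or at 9 with two or three such patients. At about 11 of 30, removing three leaves 8/27 with a lower limit of 13.8%, above the bar. A reader might conclude that the trial would generally pass overall and fail among patients who had a response to gain, or that the primary rule is invalid. Neither follows: the first needs a total close to the minimum and an assumed number of baseline responders, and the second overlooks where the 11% comes from and the possible P1101 effect after HU withdrawal.

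**What to change.** Leave eligibility, sample size and the primary analysis as they are, and add the following to the SAP.

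- **SAP 4.3.3:** derive baseline CHR status from hematocrit, platelets and white cells at the last assessment before the first dose (the SAP 3.4 definition), plus phlebotomy in the 3 months before that dose. Tabulate it by active HU at entry. Use central values where available. Protocol 15.3.1.1 says "central laboratory assessments at Weeks 0, 12, 24, 36, and 52 will be used for determination of responder", but Appendix 1 lets Week 0 tests be omitted when screening was 7 days or less earlier, and the synopsis places the pre-treatment central sample at screening.
- **Data check:** confirm that the case report form captures dates of pre-dose phlebotomies. Protocol 14 records prior non-drug therapies but mentions dates explicitly only for medication.
- **SAP 4.3.5.1:** add, as a prespecified supportive analysis, the CHR rate at both Months 9 and 12 with exact 95% interval in patients not in CHR at baseline. Report those in CHR at baseline separately as CHR maintained or CHR lost, split into HU-treated and naive.
- **SAP 4.3.4.2 and 4.3.5.5:** restrict time to first response to patients not in CHR at baseline.

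The cost is SAP wording and one or two tables, from data largely collected already. The downside is a smaller denominator and possibly a less favourable supportive rate. If no patient enters in CHR, the table shows it and strengthens the claim.

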3.1 Groups Column

The Group "P1101" will be used in table outputs.

3.2 Study Visits/ Time-Points

Number of week and number of study visit will be included in label of study visits. The labels will be as follows: Screening, Baseline, Week 2 (V2), Week 4 (V3), Week 6 (V4), ..., Week 52 (EOT), Premature discontinuation (for End-of-Study visit of premature discontinued patients), FU (for Safety Follow-Up visit). Unscheduled visit will be labeled as 'UNS' and presented in chronological order (UNSV.c), v is visit no. and c is the times of unscheduled visit between Visit v to Visit v+1. Unscheduled visit is visit recorded as '※' in EDC.

Assessment visits will be labeled as follows: Week 12 (V7), Week 24 (V13), Week 36 (V19), Week 52 (EOT). Time-window is defined as +/- 3 days of a scheduled visit date. Deviation from the time-window will usually not be adjusted, unless specified otherwise.

3.3 Flags of Values

All the required flags will include but not be limited to, the flags of abnormal values (of vital signs, laboratory assessment, physical examination, ocular examination, lung X-ray examination, heart echo), the flag of target values achieved which defined as the Values of Hematocrit <45%, Platelet count <= 400 x 10⁹/L, and WBC count <= 10 x 10⁹/L, and the flags of central assessments abnormal values. The details will be described in Listing Shell.

3.4 Baseline Values

Baseline value is defined as value of the last assessment prior to the first study drug administration.

Unscheduled and repeated assessments related to Visit 1 will be reviewed during Data Review Meeting (DRM) and questionable baseline assessments, if any, will be confirmed.

3.5 Coded Terms and Dictionaries Used

Medical terms and medications will be coded by MedDRA and WHODrug dictionary as follows:

Item Group	Dictionary (version)	Level presented in data listings*	Level used for creation of frequency tables*
Adverse event term	MedDRA (22.0 or more recent)	Reported Term, PT, SOC	PT
Previous/ concomitant medication name	WHO Drug (March 2019 or more recent)	ATC code, Preferred name	
Medical history	MedDRA (22.0 or more recent)	Reported Term, PT, SOC	PT

*PT = Preferred Term, LLT = Lowest Level Term, HLT = High Level Term, HLGT = High Level Group Term, SOC = primary System Organ Class

Level 1 = Anatomical main group, Level 2 = Therapeutic subgroup, Level 3 = Pharmacological subgroup, Level 4 = Chemical subgroup, Level 5 = Chemical substance

Current version of MedDRA and WHODrug dictionaries will be stated in the tables and listings (in title or footnote).

3.6 Study Periods

Screening period lasts from signature of informed consent to the Week 0 (Visit 1).

Treatment period lasts from Visit 1 to the "End of Treatment" visit or premature discontinuation.

End-of-Treatment (EOT) is the last visit in treatment period.

Post-Treatment Safety follow-up is visit lasting from "End of Treatment" visit (V27) or time of study discontinuation. It is also the End of Study Visit.

3.7 Study Day

Relative study day will be calculated as

Sday=date of interest – first dosing date + 1, if date of interest \geq the first dosing date.;

Sday=date of interest – first dosing date, if date of interest $<$ the first dosing date.

3.8 Adverse events

Adverse event (AE) is defined as any event recorded on "Adverse Event" page of e-CRF. Events occurred before date when the informed consent has been signed have to be recorded in "Medical History" page of e-CRF.

Serious adverse event (SAE) is any AE that is reported as serious, as indicated on the "Adverse Event" page of e-CRF.

Treatment-emergent adverse event (TEAE) / treatment emergent SAE (TESAE) is any AE / SAE occurred since date of the first study drug product administration (including that time). If onset date of AE is not complete and beginning of AE after the first drug administration cannot be excluded the AE is considered as treatment emergent. An AE, having been absent pretreatment, or worsens relative to the pretreatment state is also considered as treatment emergent. All questionable cases have to be clarified and approved before analysis.

AE leading to permanent treatment discontinuation, AE leading to dose increasing/ decreasing/ interruption and AE of special interest (AESI) are AEs as indicated on the "Adverse Event" page of e-CRF.

3.9 Previous/Concomitant Medication

Previous/concomitant medications are recorded on the 'Previous/Concomitant medications' page of the e-CRF.

Previous medication is defined as any medication that is taken only prior to the first study drug administration. This includes any medication with end date before the first study drug administration.

Concomitant medication is defined as any medication that is taken after the first study drug administration (including medication ongoing at treatment start).

Previous and concomitant medication as per this definition will be listed and tabulated separately. Concomitant medication started after date of last study drug administration will be flagged in the listings and will be tabulated separately.

3.10 Derivation and Algorithms

3.10.1 Duration of AEs

Variable used for calculation:

Variable Name \ Description

AESTDAT Start date

AEENDAT End date

Duration of AEs (number of days) will be calculated from date of AE onset and AE end using

AE_DiffDays=AEENDAT - AESTDAT;

3.10.2 Duration of treatment

Variable used for calculation:

Variable Name \ Description

EXDAT \ Date and Time of P1101 Administration

Duration of treatment (in days, weeks, months) will be calculated as follows:

```
TRT_DurDays =  
max(EXDAT of last administration) - min(EXDAT of first administration + 14);
```

```
TRT_DurWks = TRT_DurDays/7;  
TRT_DurWks = TRT_DurDays/30.5;
```

LABEL

```
TRT_DurDays = 'Treatment duration [Days]'  
TRT_DurWks = 'Treatment duration [Weeks]'  
TRT_DurMts = 'Treatment duration [Months]'  
;
```

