## 24.3 Appendix 3. Immunogenecity Sampling

Scheme	Immunogenecity Sample Collection Times Relative to Dosing a							
	Visit 1 (Week 0)	Visit 3 (Week 4)	Visit 7 (Week 12)	Visit 13 (Week 24)	Visit 19 (Week 36)	Visit 27 (Week 52)	EoS (Week 56)	Week 64, 76, 88, and 104 a
	0	0	0	0	0	0	0	0
	168 ( $\pm$ 24)							

aImmunogenicity assessment of anti-P1101 antibodies (anti-drug antibodies; ADA) will be measured at before the first dose (Week 0), 7 days (168 ( $\pm$ 24) hr) after the initial P1101 dose, Week 4, 12, 24, 36, and at End of Treatment (EoT; Week 52), and at the EoS/Follow-up visit (28 days after the final P1101 drug administration at the EoT visit). Blood samples will be collected from the subject confirmed positive for P1101 ADA at EoS visit every three months until ADAs return to baseline levels or up to 12 months.

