3.10.3 Exposure of P1101 Administration

Variable used for calculation:

Variable Name \ Description

EXSTDTC = min (EXDAT, Date and Time of P1101 Administration)

EXENDTC = max (EXDAT, Date and Time of P1101 Administration)

Treatment Exposure [days] = EXENDTC – EXSTDTC + 14,

Maximum Dose Level [ug]: sorting by unique subject id and use the proc sql to choose the maximum dose level in each subject,

Cumulated Dose [ug]: sum of all used dose by subject,

Mean Dose Level [ug/4 weeks]: 28 x Cumulated Dose [ug] / Treatment Exposure [days]

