4.3.1.7 Validation of statistical programming

The analyses of the primary endpoint, secondary efficacy endpoints and frequency tables of adverse events will be essential to perform double programming. The others also double programmed as applicable.

Logs of all programs used for analysis and data preparation will be checked for errors and unexpected warnings.

Any undocumented updating of study data in statistical programs instead of change in Clinical Database (DB) (or source data) is not allowed. Specifically, this refers to the cases where patients or the data are added/ changed using a statistical program rather than updating the DB. This kind of hard coding is usually proposed to correct deficiencies (missing values, wrong values, and wrong units) in the DB when these errors are detected after DB lock. No hard coding will be done.

This policy ensures integrity of clinical data, since no changes are made to the study data without appropriate documentation from the investigator sites and appropriate audit trails within the clinical trial DB.

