4.3.5.6 Duration of response maintenance

Duration of response maintenance will be calculated as number of days starting from assessment visit when the response was achieved till date (excluding) of assessment visit when the response was lost. If more response period occurred within one patient, the longest period will be used for analysis. Number of days will be divided by 30.5 and results presented in months.

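### SAP 3.10.2 derives treatment duration 28 days below the SAP 3.10.3 convention, overwrites the weeks variable with months, and never assigns the months variable

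*SAP*

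**What the plan says.** SAP 3.10.2 promises treatment duration in days, weeks and months, all from the administration date variable EXDAT.

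- Days: "max(EXDAT of last administration) - min(EXDAT of first administration + 14", followed by the closing bracket.
- Weeks: TRT_DurWks is first set to TRT_DurDays/7. The next line is "TRT_DurWks = TRT_DurDays/30.5", which assigns the same variable again.
- Months: the variable appears only in the label block, as "TRT_DurMts = 'Treatment duration [Months" and a closing bracket. No statement gives it a value.

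SAP 3.10.3 takes the minimum and maximum of the same EXDAT and sets "Treatment Exposure [days] = EXENDTC – EXSTDTC + 14". Mean Dose Level is built on that second quantity: "28 x Cumulated Dose [ug] / Treatment Exposure [days".

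SAP 4.3.5.6 shows what 30.5 stands for in this plan: "Number of days will be divided by 30.5 and results presented in months".

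**The concern.** Two adjacent sections turn the same first and last dose dates into a length of treatment, one by subtracting 14 days and the other by adding 14. Dosing is two-weekly, so adding 14 credits the interval covered by the last dose. Subtracting 14 has no comparable meaning and can give a negative duration. The double assignment then leaves a value in months under a label that says weeks, and nothing under the label that says months.

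A programmer who follows 3.10.2 literally would report a wrong duration for every patient. The relative error is largest for those who stop early, the patients for whom length of treatment matters most when safety data are read. The validation rules in SAP 4.3.1.7 make double programming essential for the primary endpoint, secondary efficacy endpoints and adverse event frequency tables. For everything else the text is "The others also double programmed as applicable". Two programmers working independently from the same faulty rule could also agree on the same wrong number.

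**Working it through.** **Inputs.** The 3.10.2 and 3.10.3 formulas are as quoted. The dosing interval is 14 days (Protocol 12.5). The month divisor is 30.5 (SAP 4.3.5.6). EXDAT is taken in whole days, with the first dose on day 0.

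**Algebra.** Let F be the first dose date and L the last.

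- 3.10.2: L - (F + 14) = (L - F) - 14
- 3.10.3: (L - F) + 14
- Difference: [(L - F) + 14] - [(L - F) - 14] = 28 days, whatever the schedule
- Against plain last-minus-first, 3.10.2 is 14 days short.

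**Last scheduled dose.** The documents leave this open. The flowchart in Protocol Appendix 1 appears not to mark P1101 administration at End of Treatment, which makes Week 50 (day 350) the last dose. Protocol Appendix 3 refers to "28 days after the final P1101 drug administration at the EoT visit", which implies Week 52 (day 364). Both are shown.

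| Last dose | L - F | 3.10.2 days | 3.10.3 days | Shortfall | Stored as weeks (3.10.2 days/30.5) | Weeks on 3.10.3 basis (days/7) |
|---|---|---|---|---|---|---|
| Week 52 | 364 | 350 | 378 | 28/378 = 7.4% | 11.5 | 54.0 |
| Week 50 | 350 | 336 | 364 | 28/364 = 7.7% | 11.0 | 52.0 |
| Week 24 | 168 | 154 | 182 | 28/182 = 15.4% | 5.05 | 26.0 |
| Week 12 | 84 | 70 | 98 | 28/98 = 28.6% | 2.3 | 14.0 |
| Three doses | 28 | 14 | 42 | 28/42 = 66.7% | 0.46 | 6.0 |
| Two doses | 14 | 0 | 28 | 100% | 0.0 | 4.0 |
| One dose | 0 | -14 | 14 | sign reversed | -0.46 | 2.0 |

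**Units.** For the Week 50 patient the first weeks line gives 336/7 = 48.0. The second line replaces it with 336/30.5 = 11.0, which is a number of months. TRT_DurMts stays empty.

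**Check of the correction.** With the 14 outside the bracket, 3.10.2 reduces to the 3.10.3 formula. A last dose at Week 50 gives 364 days = 52.0 weeks = 364/30.5 = 11.93 months. A last dose at Week 52 gives 378 days = 54.0 weeks = 12.39 months. A single dose gives 14 days = 2.0 weeks = 0.46 months.

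**The case against.** The strongest objection is about weight. SAP section 4 describes no table of treatment duration. Mean Dose Level uses the 3.10.3 quantity, and the rule on patients taking less than 80% of the prescribed dose rests on drug accountability. No endpoint, analysis population or safety rate depends on these variables. This stands, and it limits the consequence to descriptive output.

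Second, 28 days is a gap between two differently named quantities, not an absolute error. SAP 3.6 runs the treatment period from Visit 1 to the End of Treatment visit. If that visit is at Week 52 and the last dose is given there, the period is 364 days. The 3.10.2 value of 350 is then 14 days short of it, and the 3.10.3 value of 378 is 14 days long. This stands as a caution on the reference point. It does not rescue 3.10.2, which still falls short of every candidate definition.

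Third, EXDAT is described as a date and time. If it were held in seconds, the 14 would mean 14 seconds in both sections. Adding 14 on a two-weekly schedule only makes sense in days, so the day reading is the reasonable one, but the SAP should state it.

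Fourth, the days expression is pseudocode, the intent is easy to guess, and about 11 weeks of treatment on a 52-week study, or a negative duration, would be conspicuous. SAP 4.3.1.7 also requires log checks. That makes detection likely. A log check need not reveal a sign error, however, and a specification should not depend on the programmer departing from it.

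**Conclusion.** The concern holds. Followed as written, SAP 3.10.2 gives a treatment duration 28 days below the 3.10.3 convention, and 14 days below plain last-minus-first, for every patient. It stores months under the weeks label and leaves months without a value. For a patient completing treatment the shortfall is 7.4% to 7.7% of the 3.10.3 value, depending on whether the last dose is at Week 52 or Week 50. It is 28.6% for a last dose at Week 12. Durations are zero with two doses and negative with one.

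The figures assume EXDAT in whole days and doses on the planned 14-day schedule. The 28-day gap itself needs only the first assumption. The likely cause is a misplaced bracket and a copied variable name. The effect is limited to descriptive treatment duration. The primary endpoint, sample size, Treatment Exposure and Mean Dose Level are untouched. It should be corrected before programming is finalised.

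**What to change.** Replace the derivations in SAP 3.10.2 with:

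- `TRT_DurDays = max(EXDAT) - min(EXDAT) + 14`
- `TRT_DurWks = TRT_DurDays/7`
- `TRT_DurMts = TRT_DurDays/30.5`

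State in 3.10.2 and 3.10.3 that only the date part of EXDAT is used, so that the 14 is in days. The two sections then give the same number.

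A separate minor item can be corrected in the same revision. SAP 3.10.4 bands HADS scores as 11–14 moderate and 15–21 severe, whereas Protocol 15.3.1.5 uses 11–15 and 16–21. Only a subscale score of exactly 15 changes category, but the two tables should be reconciled.

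The cost is three lines of code, two lines of the HADS table and a clarifying phrase on EXDAT. No new data are needed and no other analysis changes.
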